Subjects with documented stable disease or an objective response may continue to receive therapy at the same dose and schedule until disease progression or unacceptable toxicities occur, or if other withdrawal criteria are met. Regardless of the duration of the study treatment, all subjects who develop early progressive disease (PD) per RECIST Version 1.1[2] prior to response evaluation will be considered to have progressed on study. Once discontinued, all subjects are to be followed for evidence of delayed effects of study drug for a minimum of 30 days from the last dose of study drug. After the 30-Day Follow-up visit, subjects will be contacted once every 3 months by the sites to collect long-term survival data. Additional contacts may be made to support key analyses, such as the analysis of overall survival at the time of the final PFS analysis, and the final analysis of OS.

Subjects experiencing unacceptable toxicities will be discontinued from further study treatment. Subjects with radiological evidence of progressive disease (per RECIST Version 1.1) per investigator/local radiology assessment should continue treatment until progressive disease is verified by an independent radiologist. An independent safety monitoring committee (SMC) will monitor the safety data from this study on a periodic basis.

Safety assessments are performed on an ongoing basis. The following procedures and evaluations can be collected at unscheduled visits as needed: electrocardiogram (ECG), physical examination, Eastern Cooperative Oncology Group (ECOG) performance status, hematology, serum chemistry, coagulation parameters, thyroid function tests, urinalysis, pregnancy tests, vital signs, tumor assessment, and survival status. Data from unscheduled assessments of the safety endpoints listed above will be included in data listings but not table summaries. For a complete schedule of planned assessments, please refer to Table 1 and/or Section 7 of the study protocol.

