4.2 General Presentation Considerations

'Baseline' is defined as the last observation on or before Cycle 1 Day 1. Baseline assessments should occur within 7 days of Cycle 1 Day 1. 'End of Treatment' is defined as the last available observation up to 7 days after the last dose of study treatment. 'End of Study' is defined as the last available observation after 'End of Treatment'.

Durations are calculated as the stop date minus the start date plus one.

For elapsed time (e.g. time since the initial diagnosis) if the reference date is on or after the event date, then the elapsed time is the reference date minus the event date plus one. If the reference date is before the event date then the elapsed time is the reference date minus the event date.

Unscheduled assessments (laboratory data, ECG, or vital signs associated with nonprotocol clinical visits or obtained in the course of investigating or managing adverse events) will be included in listings, but not summaries. If more than one laboratory value is available for a given visit, the first valid observation will be used in summaries and all observations will be presented in listings. If it is not possible to determine which is the first measurement due to missing times then the average of all measurements for that time point will be used as the value for that time point.

Continuous data will be summarized in terms of the mean, standard deviation (SD), median, minimum, maximum, and number of observations, unless otherwise stated. Continuous data that are expected to be skewed will be presented in terms of the maximum, upper quartile, median, lower quartile, minimum, and number of observations. The minimum and maximum will be reported to the same number of decimal places as the raw data recorded in the database. The mean, median, lower quartile, and upper quartile will be reported to one more decimal place than the raw data recorded in the database. The SD will be reported to two more decimal places than the raw data recorded in the database. In general, the maximum number of decimal places reported shall be four for any summary statistic.

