4.8.4 Clinical Laboratory Evaluation

Local laboratories will be used for laboratory safety evaluations in this study. For a list of the parameters to be evaluated, see Section 3.2.2 of this SAP. Laboratory normal ranges will be provided by the local laboratory. For parameters where an NCI CTCAE v.4.03 scale exists, laboratory results will be graded according to the NCI CTCAE v.4.03 severity grade. For parameters for where an NCI CTCAE v.4.03 scale does not exist, an indicator of whether the value is below, within, or above the normal range will represent severity instead.

All laboratory values will be reported in SI units.

Summaries for each laboratory parameter will be presented by treatment arm and visit. For by-visit summaries, the first non-missing assessment (including repeat assessments) recorded at each visit will be used. Optional laboratory parameters will not be summarized by treatment arm, only listed.

For laboratory values reported as a character value, such as <40, will be transformed into numerical values for summary reasons by following the specified guidelines. If a laboratory value is reported using the less than symbol, '<', 0.10 will be subtracted from the original numeric value. If a laboratory value is reported using the greater than symbol, '>', 0.10 will be added to the original numeric value.

Observed and change from baseline values in laboratory test results will be analyzed using descriptive statistics (except for parameters with categorical results, which will use frequencies and percentages). Change from baseline will only apply to post-baseline assessments for parameters with continuous results. For each lab parameter at each time point, the difference in mean changes from baseline (tivozanib – sorafenib) using a rank-

sum test will be presented along with the 95% CI. Laboratory results will also be summarized by maximum CTC grade or by worst severity, depending on the parameter.

Shifts in grade from baseline to each post-baseline visit will be summarized by treatment arm. The maximum shift (across all visits) from baseline will also be summarized by treatment arm. If needed, significance of shifts in laboratory parameters may be further evaluated within each treatment arm using a generalized McNemar's test.

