4.8.5 Vital Signs, Physical Findings and Other Observations Related to Safety

A description of vital sign parameters, ECG results, ECOG performance status, and physical examination can be found in Section 3.2.2 of this SAP.

Summaries for each vital sign parameter will be presented by treatment arm and visit. Observed and change from baseline values in vital sign results will be analyzed using descriptive statistics. Change from baseline will only apply to post-baseline assessments. For each vital sign parameter at each time point, the difference in mean changes from baseline (tivozanib – sorafenib) using a rank-sum test will be presented along with the 95% CI.

Shifts in ECG results, ECOG performance status, and physical examination from baseline to each post-baseline visit (where available) will be summarized by treatment arm. The maximum shift (across all visits) in ECG results and ECOG performance status from baseline will also be summarized by treatment arm.

For systolic blood pressure (SBP) and diastolic blood pressure (DBP), observed values will be classified as markedly abnormal (MA) or not markedly abnormal (NMA). The criteria for determining MA values are as follows:

- SBP <=80 mmHg or >=180 mmHg
- DBP <=50 mmHg or >=105 mmHg

The number and percentage of subjects with MA change values will be summarized for each vital sign parameter by treatment arm and visit.

By-subject listings of vital sign data, ECG results, ECOG performance status, and physical examination results will be provided by treatment arm.

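### The SAP bars unscheduled safety values from all summaries and makes no exception for its maximum-grade, worst-severity and maximum-shift tables, so read literally those tables can under-record the worst observed result

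*SAP*

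**What the plan says.** The exclusion appears twice. SAP 4.2 covers laboratory, ECG and vital-sign values from visits outside the protocol schedule, and also values "obtained in the course of investigating or managing adverse events) will be included in listings, but not summaries". SAP 3.1 lists the assessments that may be done at unscheduled visits, ECOG status among them, and adds: "Data from unscheduled assessments of the safety endpoints listed above will be included in data listings but not table summaries". Neither statement is limited to by-visit tables.

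The worst-value tables come later. SAP 4.8.4 states: "Laboratory results will also be summarized by maximum CTC grade or by worst severity, depending on the parameter". It continues, for laboratory shifts: "The maximum shift (across all visits) from baseline will also be summarized by treatment arm". SAP 4.8.5 has the parallel sentence: "The maximum shift (across all visits) in ECG results and ECOG performance status from baseline will also be summarized by treatment arm". None of these says whether unscheduled values count.

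The choice among several values at one visit is also stated in two ways. SAP 4.2 says: "If more than one laboratory value is available for a given visit, the first valid observation will be used in summaries". SAP 4.8.4 is narrower: "For by-visit summaries, the first non-missing assessment (including repeat assessments) recorded at each visit will be used". Protocol 14.3.5 takes the first laboratory observation when a test is repeated, and does not limit this to by-visit tables.

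**The concern.** Leaving unscheduled values out of by-visit means and shifts is sensible, because it keeps each time point comparable. A maximum-grade or maximum-shift table has another purpose: to show how bad the result became in each subject. The protocol expects extra tests exactly when something has gone wrong. Section 7.1 asks for more frequent hematology after clinically significant hematologic toxicity, section 7.1.9 provides for unscheduled laboratory tests and ECGs, and section 18.8 requires corroborative tests for unexplained laboratory abnormalities. A rule that removes those tests from the worst-value tables works against their purpose.

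Comparing safety and tolerability is a secondary objective. What is at stake is the completeness of the laboratory, ECG and ECOG summary tables in both arms.

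**Working it through.** The plan gives no figure to reproduce. The check compares the passages and counts scheduled assessments.

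**1. Which worst-value tables does the exclusion reach?**

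| Summary | SAP section | Refers to all visits? | Exception for unscheduled values? | Excluded by |
|---|---|---|---|---|
| Laboratory maximum grade / worst severity | 4.8.4 | No | None | 3.1 and 4.2 |
| Laboratory maximum shift | 4.8.4 | Yes | None | 3.1 and 4.2 |
| ECG maximum shift | 4.8.5 | Yes | None | 3.1 and 4.2 |
| ECOG maximum shift | 4.8.5 | Yes | None | 3.1 (4.2 does not name ECOG) |

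Vital signs have no maximum table; the markedly abnormal blood-pressure summary in 4.8.5 is by visit.

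**2. Scheduled ECGs (Protocol 7.1.1 to 7.1.8 and Table 1).** Screening: 1. Cycle 1 Day 1, Cycle 1 Day 15, Cycle 2 Day 1 and later cycle visits: 0. End of Treatment: 1. 30-day follow-up: 1. Scheduled post-baseline ECGs are therefore 1 + 1 = 2, and none falls between first dose and End of Treatment.

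Two is not a ceiling on what can enter the table. SAP 4.2 says that End of Treatment "is defined as the last available observation up to 7 days after the last dose of study treatment", and defines End of Study as the last observation available after that. Protocol Table 1, footnote r, also lets an assessment within 3 days of the End-of-Treatment visit stand in for it. An ECG done near or after the end of treatment could fill one of these slots. One done in mid-treatment normally could not.

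**3. Scheduled laboratory draws (Protocol 7.1.2 to 7.1.6).** Nominal days are 1, 15 and 29, then every 28 days.
- Cycle 1: 15 − 1 = 14 and 29 − 15 = 14 days.
- From Cycle 2: 28 days.
- Thyroid tests (Cycle 2, then even-numbered cycles): 2 × 28 = 56 days.

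These are nominal spacings, not upper bounds. Table 1 gives the visit window in days, Protocol 7.1 gives it in working days, and Protocol 7.2.1 and 7.2.2 allow for a delayed Day 1.

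**4. Repeat values at a scheduled visit.** Under the first-value rule of SAP 4.2, which covers summaries in general, a worse repeat at the same visit is dropped. Under 4.8.4 that selection applies only to by-visit tables. The two sections give different answers for a maximum-grade table.

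**5. What cannot be computed.** The exclusion loses information only when an unscheduled value is worse than every value retained. The documents give no frequency of unscheduled testing and no duration of abnormalities. Neither a number of affected subjects nor a probability of missing a peak can be derived.

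**The case against.** The best defence has four parts.

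- *SAP 4.2 is a general default, and the later, specific sections refer to all visits.* Protocol Table 1 does have an unscheduled column, so this reading is possible. But the phrase is absent from the maximum-grade and worst-severity sentence, and it does not clearly displace two explicit exclusions. If the sponsor intends this reading, the passages still need reconciling.
- *Scheduled-only tables are a legitimate choice in an open-label trial, because event-driven testing may differ by arm.* This stands as a real downside of the change. It can be handled by disclosing the counts.
- *The adverse-event tables already do this work.* In part they do. Protocol 10.1 and 12.1.1 send clinically significant laboratory changes, and other objective findings meeting stated criteria, to adverse-event reporting. SAP 4.8.2 tabulates treatment-emergent events by maximum CTCAE grade, and 4.8.4 lists all laboratory values with abnormal ones flagged. But entry into the adverse-event tables depends largely on the investigator's judgement, and a listing does not correct a summary table.
- *The lack of on-treatment ECGs comes from the protocol schedule, not from the SAP.* This is correct. The SAP change would add only ECGs that were done for other reasons.

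A reader might also infer that the rule favours one arm, since Day 1 draws from Cycle 2 follow tivozanib's nominal week off while sorafenib is continuous. The documents do not support that inference: they give neither the size of such an effect nor how unscheduled testing would differ by arm.

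**Conclusion.** The point holds as a minor defect in the wording of the SAP. Followed literally, the laboratory, ECG and ECOG worst-value tables can omit the worst result that was recorded, and the ECG table is the most exposed.

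This rests on reading the exclusions in 3.1 and 4.2 as they stand. It would be too strong to say that the SAP settles the matter and that unscheduled values will certainly be left out of every maximum-shift table, because the reference to all visits leaves that open. It would also be too strong to say that safety signals would disappear from the report: the adverse-event tables and full listings remain. The PFS, OS and response analyses are unaffected.

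The number of subjects affected and any direction between arms cannot be derived. The change is best described as a cheap improvement.

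**What to change.** - In SAP 3.1 and 4.2, limit the exclusion of unscheduled values to by-visit summaries. Limit the first-value rule in 4.2 in the same way, as 4.8.4 already does, and reconcile both with the first-observation sentence in Protocol 14.3.5.
- In SAP 4.8.4 and 4.8.5, state that maximum grade, worst severity and maximum shift (laboratory, ECG and ECOG) use all post-baseline values, whether scheduled, repeat or unscheduled, through the 30-day follow-up visit.
- Flag or exclude unscheduled values taken after new anti-cancer therapy starts. Protocol 7.2.5 allows such therapy once the End-of-Treatment visit is complete.
- Footnote values that fall beyond the 30-day treatment-emergent window. The visit's ±7-day window can reach day 30 + 7 = 37 after the last dose.
- Report the number of unscheduled assessments by arm beside these tables.

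The cost is a short SAP amendment, the reconciliation with Protocol 14.3.5, and table programming; no new data are needed. The downside is that unscheduled testing may differ between arms in an open-label trial. The by-arm counts disclose this, and the by-visit tables stay scheduled-only.

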4.3 Study Subjects

4.3.1 Disposition of Subjects

A clear accounting of the disposition of all subjects who enter the study will be provided, from screening to end of study participation. Summaries of subject disposition presented by treatment arm and overall will be provided as follows:

- Number and percentage of subjects randomized
- Number and percentage of subjects randomized by region
- Number and percentage of subjects treated (i.e. received at least one dose of study drug treatment)
- Number of subjects in the analysis populations
- Number and percentage of subjects who withdrew early from the study (including reasons for early withdrawal)
- Number and percentage of subjects who withdrew early from treatment (including reasons for early withdrawal)

By-subject listings of randomization details, visit dates, and withdrawal details (including reason for discontinuation and duration of treatment prior to discontinuation) will also be provided.

4.3.2 **Protocol Deviations**

Major protocol deviations are defined as those deviations from the protocol likely to have an impact on the perceived efficacy and/or safety of study treatments. The impact of major protocol deviations on the efficacy and/or safety results will be investigated by assessing the robustness of the study results and conclusions to the choice of analysis population (see Section 4.4 for descriptions of analysis populations), both including and excluding data potentially affected by major protocol deviations.

A subject will be classified as having a protocol deviation if one incurs an event belonging to any one of the following categories: 1) violation of the inclusion/exclusion criteria; 2) taking prohibited medications or treatments; 3) treatment misallocation; 4) violation of discontinuation criteria; 5) error in procedure and tests; and 6) missed visits (including procedures and tests).

Major protocol deviations and any action to be taken regarding the exclusion of subjects are defined in the study protocol deviation specifications. The final determination of major protocol deviations and the exclusion of subjects from any of the analysis populations will be made prior to database lock.

A summary of the number and percentage of subjects with a major protocol deviation by treatment arm as well as by type of deviation will be provided. Also, a by-subject listing of major protocol deviations will be provided.

4.4 Analysis Populations

- The intent-to-treat (ITT) population will consist of all randomized subjects; this population will be used for efficacy analysis, including primary endpoints. Subjects will be analyzed as randomized.
- The per-protocol (PP) population is defined as all randomized subjects who received at least two cycles (8 weeks) of protocol treatment, had no major protocol deviations that will confound the effects of treatment, and met all eligibility criteria. The PP population will be used as a sensitivity analysis for the assessment of the primary efficacy endpoint, and subjects will be analyzed as treated.
- The safety (SAF) population will include all subjects who received at least one dose of either study drug. Subjects will be analyzed as treated.

The efficacy summaries and analyses will be based on the ITT population. In the event that a subject is allocated the incorrect study treatment as per the study randomization list, subjects will be summarized and analyzed 'as randomized' (i.e. by randomized treatment arm). In the event that a subject is stratified incorrectly, 'randomized stratum' will be used rather than 'actual stratum'.

The safety summaries and analyses will be based on the SAF population. In the event that a subject is allocated the incorrect study treatment as per the study randomization list, subjects will be summarized and analyzed 'as treated' (i.e. by allocated treatment arm).

A by-subject listing of analysis population details will be provided. This listing will be presented by treatment arm and will include: center, subject identifier, inclusion/exclusion flag for each population, and reason for exclusion from each population.

